12.3. Data Collection

Data Sources

Data on the costs of personalised budgets will be provided by Greater Change. We will provide Greater Change and charity partners with a spreadsheet to populate for staff time and associated costs.

Data on benefits will be collected through the midline and endline surveys and monetised in line with the Manchester New Economy Model and HM Treasury guidance on economic evaluation of wellbeing.

Data Collection Procedures

Data will be collected through surveys administered by IFF for the impact evaluation, as well as cost data on spreadsheet templates provided by King's College London to Greater Change and the charity partners.

Data Collection Schedule

Data collection will take place at the same time as the final data collection from participants.

13. QUALITY CONTROL AND ASSURANCE

13.1. Data Quality and Assurance

Quantitative data will be collected by IFF and will be subject to their quality controls and assurance processes. Analysis of quantitative data will be subject to internal quality assurance at King's College London, with code being quality assured, as well as analytical decisions discussed among the evaluation team. The code used in the evaluation will be published to GitHub at the conclusion of the project. Management information from Greater Change and charity partners will be verified insofar as this is possible by collecting some fields in common between the two organisations. Analysis will then be quality assured by [name], Director of Evaluation at the Policy Institute, who is not a part of the evaluation team and can provide more independent oversight prior to external peer review.

Qualitative data will be quality assured via a random audit of the coding of interviews and focus groups, by randomly selecting a subsample of these to be blindly recoded by another member of the research team.

13.2. Protocol Deviations and Non-Compliance

All deviations from the trial protocol will be recorded in a deviations log associated with the trial. This will include non-adherence to randomisation, deviations in the data collection, changes to the eligibility criteria, and any changes to the analysis necessitated by unforeseen circumstances. This deviations log will be shared between King's College London, Greater Change, and CHI, and will be updated by all organisations as deviations occur. Prior to analysis taking place, the evaluation team will consider these deviations and whether they necessitate changes to the analysis. If they do, a protocol addendum will be written by the evaluators and reviewed by CHI prior to publication, and prior to any analysis taking place. This follows the process laid out by Anders et al (2017), for evaluations of complex interventions. The full (anonymised) deviations log will be published as an appendix to the final evaluation report.

14. REGISTRATION

14.1. Register

Open Science Framework (OSF) link: https://osf.io/3f427.

15. ETHICS

15.1. Ethical Approval

This project has been reviewed by the King's College London Social Sciences and Public Policy Research Ethics Committee and has been authorised with reference: HR/DP-23/24-40521.

15.2. Informed Consent

Participants will be provided with a participant information sheet at the outset of the project, giving them details of what their participation will entail. Greater Change will collect consent from participants. They will then be contacted by Greater Change to clarify any questions about the trial and record verbal consent. After 48 hours, researchers from IFF will reach out to the participant to obtain baseline data. Participants will have one week from the date of data collection to withdraw their consent prior to randomisation.

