5.2. Study Design

Study design details

This trial is a parallel randomised controlled trial with randomisation at the level of the individual participant and with data collection at three time points. Randomisation will occur on a 1:1 ratio, with stratification at the level of the charity partner.

Allocation

Randomisation will be conducted by IFF. IFF Research's approach to randomisation for the two-arm RCTs is 1:1 randomisation at the individual level. This will offer the most reliable estimates because, at the point of randomisation, all important factors would be balanced across the intervention and control condition and the effects can be securely attributed to the trial, within standard statistical tolerances.

To account for rolling participant recruitment to the trial, IFF will use a sequential individual randomisation stratified by charity partner, and with blocks of four samples in each block. In each block of four participants, two would be randomly allocated to the treatment group and two would be randomly allocated to the control group. Since we

do not know the exact number of trial participants, and this is subject to change, we do not know how many blocks we will end up with in the trial. The randomisation algorithm is coded into the baseline survey script; participants will be automatically randomised upon submission of the survey.

Once participants are randomised, we will download the data and check that the randomisation has worked as it should statistically. We will then send through the list of unique IDs that have been assigned to each group to Greater Change, so they know who to deliver the treatment to. Greater Change will then inform the charity partner and the charity partner will inform the participants themselves.

Intervention

After being referred by partner charities, participants allocated to treatment will get support from caseworkers to decide on a plan for them to stop them experiencing homelessness. The caseworker and the client define together what they need (e.g. work tools, driver's licence or secure a deposit), and the amount needed (£4,000 on average). When the funds are made available, the caseworker is responsible for purchasing what was defined in the client's plan.

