6.3. Enrolment

Participants will be enrolled in the trial if they consent to do so and provide their baseline data to IFF. We anticipate enrollment starting in August 2024 and continuing for 5 months.

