10.3. Primary Analyses

Analytical approach

Our main analytical approach for our primary analysis is regression analysis, which will be conducted on an intention-to-treat, complete cases basis. For our main housing outcomes, housing stability and perceived housing quality and satisfaction, measured via Residential Time Line Follow Back Inventory and the OMRA tool, we will conduct a linear regression, evaluated at the mean. Formally, this will be an autoregressive (AR-1), model, specified as:

$$Y_{ipt} = \alpha + \beta_1 Y_{ip0} + \beta_2 B_i + \beta_3 X_i + \beta_4 P_p + u_i$$

Where:

 Y_{ipt} is the value of the respective outcome measure (housing stability and perceived housing quality and satisfaction), for participant i at time t (endline in the primary analysis), referred by charity partner p.

 α is a regression constant

 Y_{i0} is the baseline value of the outcome for participant i in charity partner p.

 B_i is a binary treatment indicator set to 1 if participants are treated and zero else.

 X_i is a vector of participant demographic characteristics including gender (operationalised as a trinary variable) and age (operationalised as a categorical variable with 7 values including prefer not to say).

 P_p is a vector of charity partner fixed effects, reflecting that charity partner is a stratification variable.

 u_i is an error term.

This analysis will be conducted with two values of the time indicator, at the midline and endline data collection points, in both cases using the baseline data at time 0 as a control. Uncertainty will be reported through confidence intervals at p-values. We will report the binary indicator of whether the treatment effect is statistically significant, as well as present the p-value continuously and the confidence intervals.

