16.3. GDPR Compliance

All data will be held according to the King's Data Protection Policy and Procedures, and where relevant, those of IFF, who manage the data collection for this trial. All data collection will adhere to ethical practice ensuring the confidentiality of information shared and the secure handling of data in accordance with the General Data Protection Regulation (GDPR) and King's Data Protection Policy. Participant data will not be transferred outside the EU. The legal basis for processing data in this trial is a 'public task'.

Greater Change will explain the study and obtain and document UK GDPR-compliant consent to pass participants' contact details to IFF Research.

Prior to being contacted to enrol, participants will be provided with a Participant Information Sheet (PIS) by their delivery partner caseworker, which will explain the reason for collecting and processing their data, detail how long it will be stored for and if/how it will be shared with other parties and will provide them with the mechanism to ask that their data be removed or to raise a complaint. They will then provide opt-in consent to their data being processed as outlined in the PIS.

Response data will be held separately from contact details, with access to each folder limited to those who have a legitimate need to access that data. Participant data will be linked using a pseudonymous ID number, with the matching key stored in a separate folder accessible only to the leader researcher at IFF or a nominated delegate. Except where necessary for the collection of IPE data, King's College London researchers will not have access to participant contact details.

The research will end in December 2026 and personal data will be retained by King's until 31 March 2027, to enable post-study follow-up with participants. It will then be permanently deleted. Participants will be able to withdraw their personal data from the study at any time until its permanent deletion. If a participant withdraws and does not respond on whether they approve for their data to be retained, their anonymous data will be deleted. Demographic records or survey item responses will be removed or censored if there is a risk that they might enable the identification of the participant.

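### Section 15.2 promises a week to withdraw before randomisation, but section 5.2 randomises the moment the baseline survey is submitted

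*Protocol*

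**What the plan says.** Section 15.2 sets the order of events. Greater Change records verbal consent, then: "After 48 hours, researchers from IFF will reach out to the participant to obtain baseline data". The next sentence is: "Participants will have one week from the date of data collection to withdraw their consent prior to randomisation". The data collection that starts the clock is therefore the baseline survey.

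Section 5.2 (Allocation) gives a different order: "The randomisation algorithm is coded into the baseline survey script; participants will be automatically randomised upon submission of the survey". Section 6.3 agrees with 5.2 in having no waiting step: "Participants will be enrolled in the trial if they consent to do so and provide their baseline data to IFF".

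After allocation, section 5.2 has the data downloaded and checked and the ID lists sent to Greater Change. It continues: "Greater Change will then inform the charity partner and the charity partner will inform the participants themselves". Section 4.1 instead has Greater Change inform candidates directly. Neither section holds back disclosure until a week has passed.

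Two other provisions bear on what happens to a withdrawer. Section 10.3 describes the primary analysis as one "which will be conducted on an intention-to-treat, complete cases basis". Section 16.3 says: "If a participant withdraws and does not respond on whether they approve for their data to be retained, their anonymous data will be deleted".

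**The concern.** The moment of randomisation fixes who belongs to the randomised population. On the wording of 15.2, someone who withdraws on day 3 was never randomised. On the wording of 5.2, the same person has been in an arm for three days. The protocol does not say how that person is counted.

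Two things are at stake. The first is the consent statement. Section 15.4 describes participants as potentially vulnerable and possibly feeling pressure to take part, and they are told of a step that the scripted design does not provide. The second is the denominator. A withdrawal made after allocation should appear in the flow diagram and attrition table under its arm. If the record is deleted under 16.3 and no count is kept, it cannot appear there, in the balance tables of section 10.2, or in the missingness regression of section 10.9. If such losses also differed by arm, the comparison could be biased in a way the planned missing-data work could not detect.

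**Working it through.** **1. Timing, side by side.**

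| Item | Section 15.2 | Section 5.2 |
|---|---|---|
| Baseline survey submitted | day 0 | day 0 |
| Randomisation | after the one-week window, so day 7 or later | day 0, automatic |
| Status of a withdrawal on days 0 to 7 | before randomisation | after randomisation |

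A deliberate pause between completing and submitting the survey would reconcile the two, but neither section mentions one.

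**2. The plan's own power figures.** Inputs from Table 7: 180 per arm, pre/post correlation 0.6, two-sided alpha 0.05, power 0.8.

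MDES = (1.960 + 0.842) × √(1/n₁ + 1/n₂) × √(1 − 0.6²), where √(1 − 0.36) = 0.8.

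- 180 per arm: 0.2363 (stated 0.236)
- 135 per arm (25% attrition): 0.2728 (stated 0.273)
- 117 per arm (35% attrition): 0.2930 (stated 0.293)

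All three reproduce. None depends on when randomisation occurs, so reconciling the sections leaves them unchanged.

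**3. Illustration of size.** The protocol gives no early-withdrawal rate, so the rates below are assumptions. Suppose a fraction w of one arm only is lost in the first week, and those lost differ by d SD from those retained in that arm. The full-arm mean is the retained mean plus w × d, so the bias is w × d. The range shown is d = 0.25 to 1.0. The MDES column also applies the planned 25% attrition, for example n₂ = 180 × 0.95 × 0.75 = 128.25 at w = 5%.

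| w, one arm only | People of 180 | MDES | Bias, SD | Bias as share of 0.273 |
|---|---|---|---|---|
| 0% | 0 | 0.273 | 0 | 0 |
| 2% | 3.6 | 0.274 | 0.005 to 0.02 | 2% to 7% |
| 5% | 9 | 0.276 | 0.0125 to 0.05 | 5% to 18% |
| 10% | 18 | 0.280 | 0.025 to 0.10 | 9% to 37% |

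Power hardly moves. Any harm is bias, and only where loss depends on arm: if both arms lose the same fraction of similar people, the two w × d terms cancel.

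**4. Can loss depend on arm?** Only if participants learn their allocation before the week ends. Section 5.2 puts several steps between allocation and disclosure (download, check, list to Greater Change, charity partner, participant) but gives no timing for them. Early disclosure is neither stated nor prevented.

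**The case against.** A reader might infer that first-week withdrawers are treated as never randomised, and so fall out of the intention-to-treat set unevenly by arm, with disappointed controls leaving. The documents do not support that reading, for five reasons.

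- No section removes these people from the randomised set. Section 10.3 states intention to treat. Section 10.2 commits to reporting attrition at each wave and balance for the full baseline sample. With randomisation at submission, the baseline sample is the randomised sample. Section 13.2 adds a published deviations log.
- Complete-case analysis and the deletion rule apply to a withdrawal at any time. Moving randomisation to the end of the week would not stop someone from withdrawing after learning their arm later.
- Loss by arm needs disclosure within the week, which is undocumented.
- The direction is open. Controls are not told the amount they missed (section 4.1). It is intervention participants who are reminded after allocation that they may withdraw, and who have two weeks to reconsider before money is transferred (section 15.4).
- No rate is given, and about 0.25 × 180 = 45 people per arm are already expected to be lost by endline.

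All of this stands, and it reduces the statistical consequence to a conditional risk. It does not remove the contradiction between 5.2 and 15.2, which nothing in the text resolves. Nor does it cover deleted records: the reporting promised in section 10.2 cannot include people whose data are gone unless a count is kept.

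**Conclusion.** The contradiction is real and explicit: seven days in one section, none in the other. If the scripted procedure was followed, the promised period before randomisation did not exist and every first-week withdrawal is a post-randomisation loss. That makes section 15.2 wrong as written on a point that concerns both consent and the definition of the randomised population.

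The effect on the results cannot be sized from the protocol. It is nil if nobody withdrew in the week. Bias is unlikely if allocation was disclosed only after the week closed. Under the assumed one-arm losses of 2% to 10%, bias runs from 0.005 to 0.10 SD in either direction. No stated sample size or MDES changes. The conclusion assumes that the script ran as section 5.2 describes. I could not see the flow diagram in section 6.4, but a waiting step drawn there would not remove the conflict in the text.

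**What to change.** Reconcile the two sections by correcting 15.2 (and the diagram in 6.4, if needed) to match the procedure actually run, through the addendum route in section 13.2 and before analysis, which Table 4 places in February 2026. The addendum should:

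1. State that everyone the script randomised counts in the flow-diagram and attrition denominator of their arm.
2. Keep an anonymous count by arm where records are deleted under 16.3. Such people can be counted but not analysed.
3. Report first-week withdrawals by arm, and by whether allocation had been disclosed at the time.

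The cost is a few sentences and a tally.

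For any participant not yet enrolled, run the allocation step, or release its result, only after the week has closed. That delays delivery by about one week. It is probably too late for most of the trial: baseline collection was planned for August to December 2024, and this version is dated 17 June 2025.

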15.3. Ethical Challenges

Key ethical issues relate to the risk of harm to participants, which is mitigated through our safeguarding protocols; the need to conceal the quantum of money on offer to minimise the risk of undue influence to participate; and the proportionality of data collection and compensation for the same.

15.4. Risks

The present research involves participants who are vulnerable or may be at risk. Per the CARE Act (2014), an 'adult at risk':

- Has needs for care and support (whether or not the Local Authority is meeting any of those needs);
- Is experiencing, or at risk of, abuse or neglect; and
- As a result of those care and support needs, are unable to protect themselves from the risk of, or the experience of abuse or neglect.

While not all prospective participants will be classified as an adult at risk, it is probable that many individuals in contact with the partnering charity organisations, who may be considered for inclusion in the research, will fall into this category. Although most individuals in this category are likely to be ineligible for the research owing to the inclusion and exclusion criteria, there may be some adults at risk in the group of prospective participants.

Prospective participants will be referred to the study by a delivery organisation that they are currently receiving housing and other support from. Participants may consider themselves dependent on the organisation referring them to participate and therefore may feel pressure to agree to participate in the research.

We will take the following steps to mitigate risks to participants arising from their vulnerability.

Screening

 Any prospective participant where there is a concern that receiving additional financial assistance poses a risk of harm will be excluded.

This judgement will be made by the charity partners and Greater Change. Although we are not providing a prescriptive list of reasons to exclude a participant, this might include that they are deemed to be at high risk of financial exploitation.

Pressure to participate

- It is particularly important, given that participants may perceive themselves to be dependent on the delivery organisations, that they do not feel under pressure to participate in the research as a result of this. Greater Change will be given a script which they use to explain the research. This script emphasises that individuals are under no pressure to participate if they do not wish to and that doing so will not impact the individual's standing with the charity partner, or their access to other services and support.
- We are conscious that a personalised budget in the region of £4,000 may be considered an undue incentive to participate. We have proposed not to inform participants of the value of the additional financial assistance until they are allocated to the intervention and have provided a briefing for delivery organisations to inform intervention participants, which emphasises that participants do not have to accept the assistance, and reminds them that they can withdraw from the research at any time. In addition, participants will have 2 weeks to consider whether they still wish to participate, before the agreed money is transferred to the charity partner by Greater Change. If they decide to withdraw after the money is transferred or has been spent, they will not have to return the financial assistance or whatever was purchased with it.

Intervention and support

- People experiencing homelessness periodically receive additional finance via support organisations or as a result of Universal Credit back-payments. If they are engaged with a partnering charity organisation, then they receive support to think about how they wish for the funds to be spent, and monitoring to respond to risks of harm arising from receiving a personalised budget. Participants who receive a personalised budget will have more notice that they are receiving it (up to three months) and more support to plan how they would like to use the funds, than they might for other types of finance they might receive. Because the money is not given directly to participants, but is used by charity partners to purchase what has been agreed, this poses less risk to participants than if they received the money directly themselves.
- Partnering charity organisations will ensure that participants are receiving business-as-usual ongoing support throughout the trial period, as well as support around the receipt of the financial assistance, consistent with the delivery partner's service delivery model. Participants will receive this support regardless of whether they decide to withdraw from the research. Administrative data captured from delivery partners will allow us to understand what other financial and material support people will have received, while our interviews with both treatment and control groups will allow us to

identify any differences in the non-personalised budgets support received by the two groups.

Questionnaires and interviews

- Individuals such as those who are in scope for the research are
 frequently asked questions similar to those in the questionnaires, by
 support workers, Greater Change and local partnering charities. We
 have worked with associates with lived experience of homelessness
 and academic partners to avoid survey instruments that, in their
 experience, are distressing for people experiencing homelessness.
- Participants will be regularly reminded that they have the right not to answer questions without having to give a reason, and that they are able to withdraw from the research at any time. Participants who withdraw will not have to give back the item that was purchased with the personalised budget (if they have received it), and their ability to access support from the partnering charity organisation and other services will not be affected.

Safeguarding

- A risk and safeguarding protocol (Annex G) has been developed which
 covers how risk of harm identified during the research will be handled.
 In addition, for all participants, we will ask for a named contact within
 the delivery organisation that referred them, to whom participants can
 be signposted if during the research they appear distressed. Charity
 partners have also provided lists of other organisations to which
 researchers can signpost participants, which is provided as part of the
 safeguarding protocol. Delivery partners will handle safeguarding risks
 that they identify consistent with their own safeguarding procedures.
- If the research team, Greater Change or charity partners become aware of a significant vulnerability, then a conversation will occur to consider whether the participant should be removed from the research, and how this can be done without detriment to them.

